12.3.1. Assessing Severity of Adverse Events

Adverse events will be graded on a 5-point scale according to CTCAE V5.0 (Appendix 2). Investigators will collect all CTCAE grades for AEs (for both increasing and decreasing severity). All AEs reported using CTCAE classification and graded as 4 or 5 are to be considered serious. Every effort must be made by the Investigator to categorize each AE according to its severity and its relationship to the study drug. In the event that an AE is not covered by the CTCAE, the assessment of severity will be determined by using the CTCAE general guidelines.

Grade 1	Mild: asymptomatic or mild symptoms; clinical or diagnostic observations only; intervention not indicated.
Grade 2	Moderate: minimal, local, or noninvasive intervention indicated; limiting age- appropriate instrumental activities of daily living (ADL).
Grade 3	Severe or medically significant but not immediately life-threatening: hospitalization or prolongation of hospitalization indicated; disabling; limiting self-care ADL.
Grade 4	Life-threatening consequences: urgent intervention indicated.
Grade 5	Death related to AE.

An AE that is assessed as severe should not be confused with an SAE. Severity is a category used for rating the intensity of an event (as in "mild," "moderate," or "severe"). See Section 12.2.1.2 for the definition of an SAE.

12.3.2. Outcome Categorization

The outcome of AEs may be classified as resolved, resolved with sequelae, unresolved or fatal.

All treatment-related AEs will be followed to resolution (the subject's health has returned to his/her baseline status or all variables have returned to normal), or until an outcome is reached, stabilization occurs (the Investigator does not expect any further improvement or worsening of the event), or the event is otherwise explained, regardless of whether the subject is still participating in the study. Where appropriate, medical tests and examinations will be performed to document resolution of the event(s).

12.4. Reporting Adverse Events

All AEs will be recorded from the signing of consent form until 30 days following the last study drug administration. All SAEs must be reported to Sponsor within one business day of the first awareness of the event. The Investigator must complete, sign and date the SAE pages, verify the accuracy of the information recorded on the SAE pages with the corresponding source documents, and send a copy to Sponsor. Any SAEs considered possibly or probably related to the investigational product and discovered by the Investigator at any time after the study should also be reported.

A copy of all additional follow-up information, if required or available, should be sent to Sponsor within one business day of receipt and this should be completed on a follow-up SAE form, placed with the original SAE information, kept with the appropriate section of the eCRF and Investigator Study File.

Epizyme is responsible for notifying the relevant regulatory authorities of certain events. It is the Principal Investigator's responsibility to notify the IRB or IEC of all SAEs that occur at his or her site in accordance with IRB/ IEC guidelines. Investigators will also be notified of all unexpected, serious, drug-related events (7/15 Day Safety Reports) that occur during the clinical trial or at other trials using the same study drug. Each site is responsible for notifying its IRB or IEC of these additional SAEs.

12.4.1. Reporting of Adverse Events of Special Interest

All potential and identified AESIs, irrespective of their relationship to study drug, must be reported as soon as possible, but no later than 24 hours from when the Investigator becomes aware of the event.

All potential and identified AESIs must be discussed with the Medical Monitor.

12.4.2. Reporting of Pregnancy

Any pregnancy where the estimated date of conception occurs either before the last visit or within 30 days of the last dose of study drug or any exposure to study drug through breastfeeding during study drug or within 30 days of last dose of study drug must be reported.

If an adverse outcome of a pregnancy is suspected to be related to study drug exposure, this should be reported regardless of the length of time that has passed since the exposure to study drug.

A congenital anomaly, death during perinatal period, an induced abortion, or a spontaneous abortion are considered to be an SAE and should be reported in the same time frame and in the same format as all other SAEs (see Reporting of Adverse Events Section 12.4).

Pregnancies or exposure to study drug through breastfeeding must be reported as soon as possible but no later than 1 business day from the date the Investigator becomes aware of the pregnancy.

The contact information for the reporting of pregnancies and exposure to study drug through breastfeeding is provided in the Investigator Study File.

A subject who becomes pregnant must be withdrawn from the study.

12.4.3. Reporting of Special Situations

Report the special situation(s) of overdose, misuse, abuse, and/or medication error (described in Section 12.2.5) using one of the following sets of instructions according to whether the special situation occurred without any associated AEs, with an associated non-serious AE, or with an associated SAE:

Special situation(s) without associated AE(s):

• Report to Epizyme using a paper Special Situations Form following the procedures for reporting AE (Section 12.4).

Special situation(s) with an associated non-serious AE:

- Enter the non-serious event on the AE eCRF and mark the SAE field, "no". SAE related narrative fields should not be completed.
- Report to Epizyme using a paper Special Situations Form following the procedures for reporting AE (Section 12.4).

Special situation(s) with an associated SAE:

- Complete the AE eCRF per protocol for the associated SAE term ONLY (Special situations are not adverse event terms in and of themselves); complete CRF SAE fields.
- Report to Epizyme using both a paper Special Situations Form and a paper Serious Adverse Event Form following the procedures for reporting AE (Section 12.4).

12.5. Quarterly and External Safety Review: The Tazemetostat Safety Committees

Monitoring of second primary malignancies is a pharmacovigilance function. All AESIs will be fully evaluated in Quarterly Safety Review (QSR) meetings and in the External Safety Committee (ESC).

The QSR is composed of internal Epizyme subject matter experts. It is a cross-functional workgroup whose mission is to provide internal review of aggregate safety data from Epizyme global clinical and safety databases. The core committee is composed of the Epizyme Chief Medical Officer, Medical Monitor(s), Head of Nonclinical Safety, Vice President (VP) Pharmacovigilance, VP Clinical Operations, and VP Regulatory Affairs.

The primary objective of the QSR is to provide a routine, systematic, internal review of new and aggregate safety information, and to escalate newly identified concerns or issues to executive management and regulatory authorities, as applicable.

The QSR also serves in the review and adjudication of urgent safety findings identified during the course of Epizyme clinical trials and as the escalation path, as applicable.

The ESC is composed of independent oncology medical consultants; one of which serves as Chair. The ESC meets at a minimum quarterly to review new data, or on an ad hoc basis.

The purpose of the ESC is to provide independent review of clinical data for the purposes of identifying and evaluating secondary malignancy safety signals from Epizyme sponsored clinical trials. The ESC also monitors the data of those study subjects who have experienced the

tazemetostat AESIs, namely T-LBL/T-ALL, MDS, AML, and other myeloproliferative malignancies such as MPN.

Outcomes from ESC meetings may include, but are not limited to, the identification of new AESI and/or potential risk factors, the need for additional non-clinical studies or data analyses, proposals for risk mitigation measures and confirmation or revision of the tazemetostat benefit-risk. The ESC will make recommendations in the event of an AESI safety concern. Epizyme will implement recommendations which may include suspension of enrollment, protocol amendment and communication to health authorities.

13. BIOMARKER ASSESSMENTS

14. STATISTICS

This section is a summary of the planned statistical analyses of the most important endpoints including primary and key secondary endpoints. A statistical analysis plan (SAP) will be finalized prior to final database lock. Should the SAP and the protocol be inconsistent with respect to any further planned analyses, the language of the SAP is governing.

All statistical analyses will be performed by the Sponsor or designee. Sample and power calculations are based on nQuery 8.0.

Definitions of Analysis Sets

The analysis sets will be defined as follows:

- Futility Analysis Set will comprise of the first 15 subjects regardless of EZH2 status who received at least 1 dose of study drug and had tumor assessment at both baseline and Cycle 6.
- **Primary Analysis Set** will comprise of the first 43 subjects regardless of EZH2 status who received at least 1 dose of study drug and had tumor assessment at both baseline and at least one post-baseline timepoint (Cycle 3, Cycle 6, Cycle 12, Cycle 18, and Cycle 24).
- Full Analysis Set (FAS) will include all subjects who received at least 1 dose of study drug and had tumor assessment at baseline and at least one post-baseline timepoint (Cycle 3, Cycle 6, Cycle 12, Cycle 18, and Cycle 24). This will be the overall analysis set for efficacy evaluations.
- Safety Population will include all subjects who received at least 1 dose of the study drug and have at least 1 post-baseline safety evaluation, regardless of mutation status. This will be the analysis set for all safety evaluations.

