6.2. Endpoints

6.2.1. Primary Endpoint

• ORR, defined as the proportion of all subjects with WT EZH2 status achieving a CR or PR according to the 2014 Lugano Classification (Appendix 3) as assessed by Investigator and blinded independent review committee (IRC) at the following time points: Cycle 3, Cycle 6, Cycle 12, Cycle 18, and Cycle 24

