7. INVESTIGATIONAL PLAN

7.1. Overall Study Design and Plan

[figure not shown]
This is a phase 2, multicenter, open-label study of oral tazemetostat in combination with rituximab in subjects with R/R FL. Subjects will enroll into a single, open-label arm of the study where they will each be stratified based on EZH2 mutation status (MT or WT). Additionally, subjects will be stratified by previous experience with rituximab (rituximab refractory or rituximab-naïve). Stratification will occur during data analysis rather than at enrollment. This study is designed to evaluate the safety and efficacy of tazemetostat in combination with rituximab in subjects previously treated with at least 2 prior systemic lines of therapy for FL and features early futility stopping to maintain subject safety.

The first stage will enroll 15 subjects regardless of EZH2 mutational status. Futility analysis will be performed when the Cycle 6 Day 1 tumor assessment data are available for the first 15 subjects. If there are 8 or fewer responses in these 15 subjects, the study will be considered futile. Enrollment will continue during the interim futility analysis. If 9 responses or greater are seen in the initial 15 subjects, additional subjects will be accrued for a total of 54 evaluable subjects regardless of mutation status.

Based on Simon's 2-stage design, the primary analysis will occur after 43 evaluable subjects regardless of mutation status are available. Enrollment will continue during the primary analysis. Full set analysis will occur once data from 54 evaluable subjects regardless of mutation status are available.

This study includes a 28-day screening period, a 2-year (24-cycle) treatment period, and a follow-up period. During the treatment period, subjects will receive tazemetostat in combination with rituximab in 28-day cycles for the first 6 cycles followed by tazemetostat alone in 28-day cycles for the remaining 18 cycles, or until disease progression, unacceptable toxicity, or withdrawal of consent. Disease assessments will be performed at screening, Cycle 3 Day 1, Cycle 6 Day 1, Cycle 12 Day 1, Cycle 18 Day 1, and Cycle 24 Day 1.

Figure 1: Study Schema

Note: Enrollment will not stop during futility analysis or primary analysis.

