14.1. Futility Analysis

Futility analysis (FA) will be performed when the Cycle 6 tumor assessment data are available for the first 15 evaluable subjects regardless of EZH2 status. ORR, defined as the proportion of the subjects achieving a CR or PR according to the 2014 Lugano Classification (Appendix 3), will be calculated. Subjects with the best response of unknown/non-evaluable response will be treated as non-responders, (i.e., they will be included in the denominator only when calculating ORR).

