14.6. Determination of Sample Size and Criteria for Early Stopping Due to Futility

The primary objective of this study is to evaluate the ORR obtained in subjects with R/R FL and WT EZH2 status, treated with the combination of rituximab and tazemetostat. Given the historical data with single agent rituximab (McLaughlin, 1998; Leonard, 2019), the Sponsor would consider the combined regimen to be of no further interest if the ORR were 50% or less, but of considerable interest if the ORR were at least 70%.

Simon's two-stage design (Simon, 1989) will be used. The null hypothesis that the true response rate is 50% will be tested against the one-sided alternative. In the first stage, 15 subjects will be accrued. If there are 8 or fewer responses in these 15 subjects, the regimen will be considered as futile.

Subject enrollment will continue during futility analysis. If 9 responses or greater (CR + PR) are seen in the initial 15 subjects, additional subjects will be accrued for a total of 54 evaluable subjects. The Sponsor expects 80% of enrolled subjects to have WT EZH2 status. Consequently, the study will enroll approximately 43 WT subjects as well as approximately 11 MT subjects. With an estimated early dropout rate of 10%, this study estimates a total accrual of 59 subjects.

For the primary analysis, the null hypothesis will be rejected if 27 or more responses (CR + PR) are observed in the first 43 evaluable subjects regardless of mutation status. This design yields a one-sided type I error rate of 0.05 and power of 0.801 when the true response rate is 70%.

If the primary analysis is successful, full analysis will be conducted once 54 evaluable subjects are available regardless of mutation status. Subjects in the FAS will be stratified to 2 subgroups depending on their EZH2 mutation status (WT vs MT).

With an estimated 54 eligible subjects in the combined FAS, rates of individual AEs can be estimated to within at most \pm 14% (95% confidence interval). Any AE with a true rate of at least 5% is likely to be observed at least once (93% chance).

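### The Futility Analysis Set requires a Cycle 6 scan, but the 8-of-15 stopping rule is written for 15 enrolled or accrued subjects, so early progressors can fall out of the count

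*Protocol*

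**What the plan says.** Stage 1 is described in two ways.

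- **Design wording.** Protocol Section 7.1: "The first stage will enroll 15 subjects regardless of EZH2 mutational status". Section 14.6: "In the first stage, 15 subjects will be accrued. If there are 8 or fewer responses in these 15 subjects", the regimen is futile. The synopsis (Study Design and Sample Size Justification) and SAP Section 3.2.1 say the same.
- **Analysis wording.** In Section 14, Definitions of Analysis Sets, the Futility Analysis Set is the first 15 subjects "who received at least 1 dose of study drug and had tumor assessment at both baseline and Cycle 6". Section 14.1 agrees with this: "Futility analysis (FA) will be performed when the Cycle 6 tumor assessment data are available for the first 15 evaluable subjects".

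The later sets are less strict. The Primary Analysis Set is the first 43 dosed subjects who "had tumor assessment at both baseline and at least one post-baseline timepoint". The Full Analysis Set (FAS) is all dosed subjects who "had tumor assessment at baseline and at least one post-baseline timepoint". Any one listed scan is enough.

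Section 14.1 also has a rule for missing outcomes: "Subjects with the best response of unknown/non-evaluable response will be treated as non-responders". It covers subjects already in the set.

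The Table 2 footnote on tumor response assessments (Section 7.7) runs scheduled scans until loss of clinical benefit or progression. Scans continue after treatment stops only if the reason was something other than progression.

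**The concern.** A Cycle 6 scan is a condition met after dosing, and whether it is met depends partly on outcome. A subject who progresses at the Cycle 3 scan is an established non-responder but need not be scanned again. Under the Section 14 definition that subject leaves the futility set. The set is the first 15 who qualify and enrollment continues during the analysis, so a later subject fills the place. The non-responder rule does not help, because it acts only inside the set.

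The plan's own final analysis treats the same subject differently: with a Cycle 3 scan, a Cycle 3 progressor is in the Primary Analysis Set and the FAS as a non-responder. The inconsistency at stage 1 therefore does not depend on how the 50% and 70% rates were derived.

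At stake is the go/no-go decision at 15 subjects, which Section 7.1 presents as a protection for subjects. If mainly non-responders are dropped, an inactive regimen continues more often than designed.

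**Working it through.** **Inputs from the documents** (Protocol Section 14.6, SAP Section 3.2.1): null rate 0.50, target rate 0.70; stop at 8 or fewer of 15; reject at 27 or more of 43; stated one-sided type I error 0.05 and power 0.801.

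**Assumed inputs.** f is the share of treated subjects who are non-responders and lack the required scan; h is the share who are responders and lack it. The documents give neither, so a range is shown.

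**1. Reproduce the design.** P(pass futility) = sum over x = 9 to 15 of C(15,x) p^x (1−p)^(15−x). At p = 0.50 this is 9949/32768 = 0.304; at p = 0.70 it is 0.869. Adding the requirement of 27 or more of 43 in total gives exact type I error 0.0499 and power 0.804. These agree with the stated 0.05 and, closely, with 0.801. The boundaries are sound; the question is which subjects they apply to.

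**2. Would the two stage 1 definitions differ in practice?** P(at least one of the first 15 treated lacks the scan) = 1 − (1−loss)^15. At 5% loss: 1 − 0.95^15 = 0.54. At 10%: 1 − 0.90^15 = 0.79. At such losses the two definitions usually select different subjects.

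**3. Effect on the futility decision at a true rate of 50%.** The rate among those with a Cycle 6 scan is (0.50 − h)/(1 − f − h). Put this into the step 1 formula:

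| f (non-responders lost) | h (responders lost) | Rate in set | P(pass) |
|---|---|---|---|
| 0 | 0 | 0.500 | 0.304 |
| 3% | 0 | 0.50/0.97 = 0.515 | 0.347 |
| 5% | 0 | 0.50/0.95 = 0.526 | 0.379 |
| 10% | 0 | 0.50/0.90 = 0.556 | 0.470 |
| 10% | 5% | 0.45/0.85 = 0.529 | 0.389 |
| 5% | 5% | 0.45/0.90 = 0.500 | 0.304 |
| 3% | 7% | 0.43/0.90 = 0.478 | 0.245 |

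**4. Effect of the Cycle 6 condition on final type I error.** Here the first 43 treated subjects all stay in the final test and only the futility set loses subjects. Simulation (600,000 trials per case, non-responders lost) gives 0.054 at 5% and 0.057 at 10%. Rejection always needs at least 27 of 43, so the error cannot exceed that probability with no futility look, which is 0.063 at p = 0.50.

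**5. The final test is a separate matter.** Suppose the 50% null is a rate among all treated subjects and a share g, all non-responders, have no listed post-baseline scan. The rate in both sets is then 0.50/(1 − g), and exact type I error is 0.057 at g = 1%, 0.065 at 2% and 0.095 at 5%. If 50% and 70% are rates among scanned subjects, 0.05 and 0.80 stand for the 27-of-43 test. Section 14.6 ties the rates to historical single-agent rituximab data and gives no denominator.

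**The case against.** **The operative set can be identified.** Section 7.1 itself times the look by Cycle 6 Day 1 data for the first 15, and Sections 14 and 14.1 are specific. That is fair as a reading of intent. But Section 14.6, where the error rates are derived, still applies the rule to accrued subjects, and the specific definition is the one that drops Cycle 3 progressors.

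**The direction of bias is not settled.** This stands. Section 7.5 lets some progressors stay on treatment and so be scanned at Cycle 6, and a Cycle 3 responder who misses Cycle 6 is also excluded. Steps 3 and 4 show zero and downward cases. Upward bias is the more plausible direction given the scan schedule, but it is not certain.

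**Three stronger readings are tempting, and the documents do not support them.**

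- A reader might infer that the final test is shown to be anti-conservative. It is not. Sections 14 and 14.6 put 27 of 43 on evaluable subjects throughout, and inflation needs an all-treated null that the plan does not state.
- A reader might take the fall from 59 to 54 subjects (Section 7.2) as the loss rate. That is enrolled to evaluable. It may include subjects never dosed or without a baseline scan, so it does not estimate treated-but-unscanned loss.
- A reader might see a second denominator in Section 6.2.1, which speaks of the "proportion of all subjects with WT EZH2 status achieving a CR or PR". Section 14.2 names the analysis set as the wild-type subset of the FAS. An endpoint line that omits the analysis set is ordinary drafting.

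**All-treated versus evaluable is a choice of estimand.** This also stands for the final test. If the rates were set for scanned subjects, moving 27 of 43 to all treated subjects would cut power from 0.804 to 0.664 with 5% unscanned (rate 0.70 × 0.95 = 0.665). The change there must wait for the denominator to be stated.

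**Conclusion.** The stage 1 inconsistency is real and worth correcting. The futility set is conditioned on a Cycle 6 scan, the stopping rule is stated for 15 enrolled or accrued subjects, and a known non-responder can be replaced. Under the assumption that all subjects lost are non-responders, the chance that a 50% regimen continues rises by 4 to 17 percentage points at 3% to 10% loss. With equal or greater loss of responders, the effect is nil or reversed. The loss rates are assumptions.

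The condition does little to final type I error. For the Primary Analysis Set and FAS there is no demonstrated error, only a missing statement of what the benchmark rates refer to.

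The point concerns the protocol design only. SAP Sections 5.2 and 8 report early termination with 5 treated subjects and no futility or efficacy analysis, so no reported result is affected.

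**What to change.** **Futility set.** Define it as the first 15 consecutively treated subjects with a baseline tumor assessment. Count anyone without a documented CR or PR by the Cycle 6 assessment as a non-responder. Keep the 8-of-15 boundary. Use the same wording in the synopsis (Study Design and Sample Size Justification), Protocol Sections 7.1, 14, 14.1 and 14.6, and SAP Section 3.2.1.

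**Final test.** State in Section 14.6 whether 50% and 70% refer to treated or to scanned subjects. Report ORR with treated-but-unscanned subjects as non-responders alongside the evaluable analysis. If the rates refer to treated subjects, make the all-treated analysis primary. If they refer to scanned subjects, the evaluable analysis can stay primary.

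**Cost.** Wording changes and one added summary; no change to boundaries or sample size. One trade-off should be disclosed. If 70% describes scanned subjects and 5% of treated subjects have no post-baseline scan, the rate in the revised futility set is 0.665, and the chance that a good regimen passes falls from 0.869 to 0.793.
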